4.8. Criteria for Study Modifications

Part 1 consists of a 40-subject, two-cohort, single-arm evaluation of the safety of the triple combination. The Sponsor may adjust the dose and/or schedule for Cohort 2 based on the initial safety evaluation of Cohort 1A and 1B. The Sponsor will assess the data from both cohorts to determine the dose and/or schedule before beginning the randomized portion of the study.

4.9. Independent Committees

4.9.1. Independent Data Monitoring Committee

The IDMC will periodically monitor the randomized portion of the study for safety considerations. The IDMC will consist of independent reviewers who are not directly involved in the conduct of the study and will advise the Sponsor of any trends or safety issues which may impact the study and/or the study subjects. The IDMC will operate according to a charter, which the committee will review and ratify before enrollment commences. The IDMC, at a minimum, will as follows:

- Consist of at least 2 oncologists + 1 statistician, all of whom are independent from the study personnel
 - Evaluate accumulating safety data during Part 2 for all enrolled and treated subjects after 50, 100, and 150 subjects have been randomized.

4.9.2. Blinded Independent Review Committee

A BIRC will conduct a blinded review of combined positron emission tomography with computerized tomography (PET/CT) scans or CT scans performed during evaluation of efficacy during the study. An imaging laboratory will conduct the review to document response (CR, PR, stable disease [SD], or progressive disease [PD]) to therapy for all subjects with at least 1 post-baseline disease assessment. The central reviewers will be independent of the study investigators and blinded to study arm assignment. Each efficacy evaluation for every subject will be reviewed by 2 independent radiology reviewers and a clinical reviewer, with any discordance between the radiology reviewers adjudicated by a third radiologist. The committee will operate according to a charter which will be prepared prior to any efficacy analysis.

4.9.3. Independent Confirmation of Histological Diagnosis

A central pathologist will review tissue (archival or fresh) provided at baseline to retrospectively confirm the diagnosis and cell of origin. The pathologist will not be a participating investigator in the study and will operate according to a charter.

5. STUDY ASSESSMENTS

[Table 9](#) defines the timing of study events and assessments, and [Table 10](#) defines the sampling days for plamotamab ADA, cytokines, PK, ECGs, and rituximab levels. [Table 11](#) defines the sampling days for tafasitamab ADA and PK. For additional details, refer to the protocol text and study manuals.

Table 9: Schedule of Assessments

Pretreatment, Cycle 1, and Cycle 2																				
Evaluation or Procedure	Pretreatment				Cycle 1										Cycle 2					
Day	-35 to -9	-8	-4	-1	1	2	3	4	8 ± 1	9	15 ± 1	16	22 ± 1	23	1 ± 1	2	8 ± 1	15 ± 1	22 ± 1	26 ± 3
Informed consent	X																			
Review of inclusion/exclusion criteria	X																			
Inpatient status ^a				X	X	X	X	X	X	X	X	X	X	X	X					
Registration (Part 1)/Randomization (Part 2)	X																			
Plamotamab administration ^{b, c}					X				X		X		X		X		X	X	X	
Tafasitamab administration ^d		X	X		X				X		X		X		X		X	X	X	
Lenalidomide administration ^e					X	X	X	X	X	X	X	X			X	X	X	X		
Medical History ^f	X																			
Physical examination ^f	X	X		X	X		X		X ^g		X ^g		X ^g		X ^g		X ^g	X ^g	X ^g	X
Neurologic exam, including ASTCT ICANS Consensus Grading ^h	X			X	X	X	X		X		X		X		X		X	X	X	
Vital signs ^{e, i}	X	X	X	X	X	X	X	X	X	X	X	X	X	X	X		X	X	X	
Height	X																			
Weight	X	X		X					X ^g		X ^g		X ^g		X ^g		X ^g	X ^g	X ^g	
ECOG PS	X	X		X	X ^g				X ^g		X ^g		X ^g		X ^g		X ^g	X ^g	X ^g	
CBC w/ differential ^j	X	X		X	X	X	X	X	X ^g	X	X ^g	X	X ^g	X	X ^g		X ^g	X ^g	X ^g	
Chemistry panel ^j	X	X		X	X	X	X		X ^g		X ^g		X ^g		X ^g		X ^g	X ^g	X ^g	
Coagulation panel	X			X		X			X ^g		X ^g		X ^g		X ^g					
Fibrinogen				X		X			X ^g		X ^g		X ^g		X ^g					
Urinalysis with microscopy ^k	X	X		X		X			X ^g		X ^g		X ^g	X	X ^g					
HBsAb, HCV, HIV ^l	X																			
HBsAg, Hepatitis B DNA ^m	X														X					
Urine or serum β-hCG (females of childbearing potential) or serum FSH (postmenopausal) ⁿ	X	X		X					X ^g		X ^g		X ^g		X ^g					

Pretreatment, Cycle 1, and Cycle 2																				
Evaluation or Procedure	Pretreatment				Cycle 1										Cycle 2					
Day	-35 to -9	-8	-4	-1	1	2	3	4	8 ± 1	9	15 ± 1	16	22 ± 1	23	1 ± 1	2	8 ± 1	15 ± 1	22 ± 1	26 ± 3
LEN Counseling/Dosing Diary Collection	X				X										X					
Rituximab levels				X											X					
Peripheral blood for TBNK, leukocyte flow cytometry °	X	X			X	X	X		X	X	X	X	X	X	X	X				
Peripheral blood for RNA analysis °		X									X				X					
SARS-CoV-2 nucleic acid or antigen test ^p	X																			
Tumor assessment ^{q,r}	X																			X
Archival Tissue ^s	X																			
Tumor Biopsies ^t	X												X							
ctDNA Sample ^u	X				X						X				X					X
Monitor/record adverse events	X	X	X	X	X	X	X	X	X	X	X	X	X	X	X	X	X	X	X	X
Record concomitant medication	X	X	X	X	X	X	X	X	X	X	X	X	X	X	X	X	X	X	X	X
Phone/email/mail contact for progression/survival																				
12-lead ECG (supine)	X				See Table 10															
Cytokines	See Table 10																			
PK Sampling	See Table 10																			
ADA sampling	See Table 10																			

Evaluation or Procedure	Cycles 3 + and Post-Treatment																
	Cycle 3				Cycle 4			Cycle 5 and subsequent odd cycles		Cycle 6 and subsequent even cycles			Post treatment				
	Day	1 ± 1	8 ± 1	15 ± 1	22 ± 1	1 ± 1	15 ± 1	26 ± 3	1 ± 1	15 ± 1	1 ± 1	15 ± 1	26 ± 3	EOT	30 d ± 3 post-EOT	90 d ± 10 post-EOT	Follow-up Q2 mos. ± 2 weeks
Informed consent																	
Review of inclusion/exclusion criteria																	
Inpatient status ^a																	
Registration (Part 1)/Randomization (Part 2)																	
Plamotamab administration ^{b, c}	X		X		X	X		X	X	X	X						
Tafasitamab administration ^d	X	X	X	X	X	X		X	X	X	X						
Lenalidomide administration ^e	X	X	X		X	X		X	X	X	X						
Medical History ^f																	
Physical examination ^f	X	X ^g	X ^g	X ^g	X ^g	X ^g	X	X ^g	X ^g	X ^g	X ^g	X	X	X			
Neurologic exam, including ASTCT ICANS Consensus Grading ^h	X		X		X			X		X			X				
Vital signs ^{e, i}	X	X	X	X	X	X		X	X	X	X		X				
Height																	
Weight	X	X ^g	X ^g	X ^g	X ^g	X ^g		X ^g	X ^g	X ^g	X ^g		X				
ECOG PS	X ^g	X ^g	X ^g	X ^g	X ^g	X ^g		X ^g	X ^g	X ^g	X ^g		X				
CBC w/ differential	X ^g	X ^g	X ^g	X ^g	X ^g	X ^g		X ^g	X ^g	X ^g	X ^g		X				
Chemistry panel	X ^g	X ^g	X ^g	X ^g	X ^g	X ^g		X ^g	X ^g	X ^g	X ^g		X				
Coagulation panel	X ^g		X ^g		X ^g			X ^g		X ^g			X				
Fibrinogen	X ^g		X ^g		X ^g			X ^g		X ^g			X				
Urinalysis with microscopy ^k	X ^g		X ^g		X ^g			X ^g		X ^g			X				
HBsAb, HCV, HIV ^l																	
HBsAg, Hepatitis B DNA ^m	X				X			X		X					X		

Evaluation or Procedure	Cycles 3 + and Post-Treatment															
	Cycle 3				Cycle 4			Cycle 5 and subsequent odd cycles		Cycle 6 and subsequent even cycles			Post treatment			
	Day	1 ± 1	8 ± 1	15 ± 1	22 ± 1	1 ± 1	15 ± 1	26 ± 3	1 ± 1	15 ± 1	1 ± 1	15 ± 1	26 ± 3	EOT	30 d ± 3 post-EOT	90 d ± 10 post-EOT
Urine or serum β-hCG (females of childbearing potential) or serum FSH (postmenopausal) ⁿ	X ^g				X ^g			X ^g		X ^g					X	
Lenalidomide Counseling/Dosing Diary Collection	X				X			X		X						X ^v
Rituximab levels					X											
Peripheral blood for TBNK, leukocyte flow cytometry ^o	X							X					X			
Peripheral blood for RNA analysis ^o																
SARS-CoV-2 nucleic acid or antigen test																
Tumor assessment ^{q,r}							X					X	X ^w		X ^w	
Archival Tissue																
Tumor Biopsies ^t																
ctDNA Sample								X ^u		X ^u			X			
Monitor/record adverse events	X	X	X	X	X	X	X	X	X	X	X	X	X	X	X ^x	X ^x
Record concomitant medication	X	X	X	X	X	X	X	X	X	X	X	X	X	X		
Phone/email/mail contact for progression/survival																X
12-lead ECG (supine)	See Table 10															
Cytokines	See Table 10															
PK Sampling	See Table 10															
ADA sampling	See Table 10															

ADA = anti-drug antibodies; ASCTC = American Society for Transplantation and Cellular Therapy; β-hCG = beta human chorionic gonadotropin; CBC = complete blood count; C#D# = Cycle # Day #, eg, C1D1 = Cycle 1 Day 1; CRS = cytokine release syndrome; CT = computerized tomography; ctDNA = circulating tumor DNA; d = day; DICOM = Digital Imaging and Communications in Medicine; ECG = electrocardiogram; ECOG = Eastern Cooperative Oncology Group; eCRF = electronic case report form; EDC = electronic data capture; EOI = end of infusion; EOT = end of treatment; FSH = follicle-stimulating hormone; HBcAb = hepatitis B core antibody; HBsAb = hepatitis B surface antibody; HBsAg =

hepatitis B surface antigen; HCV = hepatitis C virus; HIV = human immunodeficiency virus; ICANS = immune effector cell-associated neurotoxicity syndrome; IV = intravenous; LEN = lenalidomide; mo = month; PE = physical examination; PET = positron emission tomography; PHI = protected health information; PK = pharmacokinetics; PS = performance score; Q# = every # (eg, Q2 mo = every 2 months); SAE = serious adverse event ; SARS-CoV-2 = severe acute respiratory syndrome coronavirus 2 of the genus betacoronavirus; TBNK = T-, B-, and NK cell.

- ^a Subjects are required to be admitted as inpatient for 72 hours after the first dose of plamotamab and for a minimum of 24 hours after any dose increase of plamotamab.
- ^b Plamotamab will be administered as an IV infusion [REDACTED].
- ^c For subjects who tolerate 4 consecutive infusions of plamotamab at a stable dose and schedule without CRS or an infusion reaction during the infusion or post-infusion observation period, the post-infusion observation period and vital signs assessment may be reduced from 5 hours to 2 hours.
- ^d Tafasitamab is administered as a 2 hour IV infusion. On days when both plamotamab and tafasitamab are given, the tafasitamab should be administered before plamotamab with at least 2 hours between the infusions.
- ^e Lenalidomide is administered orally once daily in the evening on Days 1 to 21 of each 28-day cycle, up to 12 cycles.
- ^f Complete medical history and PE is required at screening. For all the other time points an abbreviated, symptom-directed PE is to be performed.
- ^g May be performed the day prior to the plamotamab infusion. Results should be available and reviewed before starting plamotamab infusion.
- ^h ASTCT ICANS Consensus Grading for Adults, [Table 5](#) and [Table 6](#), must be completed at least 1 hour post-infusion, but no more than 12 hours post-infusion, on the day of plamotamab infusion. On days when no study drug infusion occurs, the assessments should be completed at approximately the same time each day (approximately 24 hours post-infusion, 48 hours post-infusion, 72 hours post-infusion, etc.). Beginning with Cycle 4, the ASTCT ICANS Consensus Grading assessments are only required on Day 1 of subsequent cycles. ICANS Grading should also be performed if clinically indicated.
- ⁱ Supine or sitting blood pressure and heart rate, body temperature, respiratory rate, and blood oxygen saturation by continuous pulse oximetry. On days of infusions, vital signs coinciding with the plamotamab dosing should be taken predose; 15, 30, and 60 minutes after start of infusion (± 5 minutes); at EOI (± 5 minutes); 15 (± 5 minutes); 30 (± 5 minutes); and 60 (± 10 minutes) minutes after EOI; and then hourly for 4 hours (± 15 minutes). Vital signs for the tafasitamab dosing should be taken predose and 30 minutes after EOI (± 5 minutes). All vital signs during infusion should be taken with subject in the same position. The pulse oximetry for blood oxygen saturation level needs to be captured with each vital sign collection; however, pulse oximetry monitoring must be maintained continuously, as practical, throughout the entire admission period for each administration of plamotamab, regardless of inpatient or outpatient status. For more information of management of oxygen saturation of 90% or lower, see [Section 4.6.1.4](#).
- ^j If performed on dosing days, the assessment should be performed prior to administration of any study drug.
- ^k Urinalysis is required; the microscopy is only required if clinically indicated.
- ^l May be performed up to 8 weeks prior to screening.
- ^m HBsAg and Hepatitis B DNA repeat testing should be performed only if HBcAb serology is positive and HBsAb serology is negative at screening. Testing for visit Days 1 at Cycle 2 and subsequent cycles should be done 1 to 3 days prior to the Day 1 visit so that results are available prior to the Day 1 dose for the subsequent cycles.
- ⁿ FSH needs only to be performed at screening for suspected postmenopausal women. If menstrual cycles are irregular, the pregnancy testing should occur every 2 weeks.
- ^o Draw prior to study drug administration. In addition, unscheduled samples, if available, may be sent to the designated central laboratory per the laboratory manual for flow and biomarker analysis. The frequency of biomarker collections may be reduced during the study based on emerging data.
- ^p SARS-CoV-2 nucleic acid or antigen test, performed locally, is to be completed and result within 7 days prior to Day -8.
- ^q PET/CT and bone marrow biopsy/aspirate (for subjects with known bone marrow involvement). All studies for the baseline assessment should be performed within 21 days prior to Day -8. After Cycle 12, perform disease assessments every 3 cycles (or Q12 weeks) up to Cycle 36 and every 4 cycles (Q16 weeks) up to Cycle 60. Any unscheduled disease assessment performed in suspicion of progressive disease must be recorded in the eCRF.
- ^r PHI-redacted tumor assessments including, but not limited to assessment reports and/or digital imaging files (DICOM) for scans/imaging, blood, and bone marrow biopsy pathology reports are to be provided to support response assessments.
- ^s Archival tissue from excisional biopsies of lymph node to be sent to the designated central laboratory as an archival block (**preferred**) or up to 43, if possible, unstained slides. Archival tissue must predate study treatment. If archival tissue is not available or is insufficient, the screening fresh tumor biopsy becomes mandatory to satisfy the inclusion criterion.
- ^t Fresh tumor biopsy will be collected at screening up to 21 days prior to Day -8. The on treatment fresh tumor biopsy performed after the fourth dose between the C1D22 and C2D1 visit. Fresh tumor biopsy is strongly encouraged but is optional and requires separate consent. The baseline sample becomes mandatory for study participation if archival tissue is not available to satisfy the inclusion criterion.
- ^u The Screening (baseline) sample will come from the submitted archival or fresh tumor biopsy sample to identify malignant clones. Samples of whole blood and plasma will be collected through C2D1; only whole blood will be collected at C2D26, C6D1, C9D1, C12D1 and EOT for the detection and quantification of ID clonotype(s) that were identified from the baseline sample.

- ^v Male subjects will be followed for 6 months, and female subjects 8 months following the last dose of study drug to confirm contraceptive use.
- ^w Subjects who complete a tumor assessment within the prior 14 days do not have to repeat the EOT tumor assessment. If a subject was removed from study for disease progression and this response data for that applicable visit is adequately documented in EDC, the post-treatment (EOT and 90 days post EOT) tumor assessments do not need to be repeated.
- ^x Treatment-related SAEs should be followed up until resolution.

Table 10: Sampling for Plamotamab Anti-Drug Antibodies, Cytokines, PK, and ECGs, and Rituximab Levels

Plamotamab PK, cytokines, and ADA, as well as ECGs, are performed for subjects in Part 1 and subjects randomized to Arm A in Part 2. All times are relative to the plamotamab infusion. On days when tafasitamab and plamotamab are administered, draw predose samples and perform ECG before the start of the tafasitamab infusion.

Study Day	Pretreatment	Cycle 1				Cycle 2		Cycle 3		Cycle 4+	Post-treatment	
	-1	1	8	15	22	1	15	1	15	1	EOT	30d ±3 post EOT
Predose	Rituximab level	pPK, Cyto, pADA ECG ^a	pPK, Cyto,	pPK, Cyto	pPK, Cyto,	pPK Cyto, pADA ECG Rituximab level	Cyto	pPK Cyto, pADA ECG	Cyto,	pPK ^b pADA ^b ECG ^b Rituximab level ^h		
During the Infusion		pPK ^c ECG ^c		pPK ^d ECG ^d								
At the end of the infusion (+/- 10 min)		pPK ECG	ECG		ECG	pPK ECG	ECG	pPK ECG		pPK ^b ECG		
7 hr post infusion (+/- 30 min)		Cyto	Cyto	Cyto	Cyto	Cyto	Cyto ^g	Cyto ^g	Cyto ^g			
24 hr post infusion (+/-2 hr)		Cyto	pPK ^c Cyto	Cyto	Cyto	Cyto	Cyto	Cyto	Cyto			
48 hr post infusion (Day 3)		pPK ^f										
Post-treatment; not timed											pPK pADA	pPK pADA

Cyto = cytokine assays; d = day; ECG = electrocardiogram; EOT = end of treatment; pADA = plamotamab anti-drug antibodies; pPK=plamotamab pharmacokinetics.

^a ECG in triplicate: obtain three ECGs each separated by 2 minutes on Day 1 only; other ECGs are single studies.

^b In all even numbered cycles only

^c 1 hour (±10 minutes) after the start of Day 1 plamotamab infusion

^d 1.5 hours (±10 minutes) after the start of third plamotamab infusion

^e 24 hours (±2 hours) after the start of the second plamotamab infusion

^f 48 hours (±4 hours) after the start of the 1st plamotamab infusion

^g Cytokine assessment is optional at these timepoints

^h Required only at Cycle 4 Day 1

Note: Predose pPK and ECG: can obtain up to 2 hours prior to the start of the infusion and can be -5 minutes before or +15 minutes after the end of infusion.

In addition to timepoints from Table 10, cytokines should also be drawn if there is clinical suspicion of CRS at any time and repeated 4 hours later.

In the event of a subject overdose, an unscheduled PK sample should be collected and sent to the designated central lab, if requested by the Medical Monitor.

Note: Rituximab level, PK, ADA, and cytokine samples are to be sent to the designated laboratory, per the laboratory manual, for analysis. All samples should be drawn within the time windows of the designated time and should be labeled with the exact, actual time of sampling.

Table 11: Sampling for Tafasitamab Anti-Drug Antibodies and Pharmacokinetics

Tafasitamab anti-drug antibodies and pharmacokinetics performed in all subjects. All times are relative to the tafasitamab infusion.

Study Day	Pretreatment	Cycle 1					Cycle 2		Cycle 3		Cycle 4+	Post-treatment	
	-8	2	9	15	16	23	1	15	1	15	1	EOT	30d ±3 post EOT
Pre-dose	tPK, tADA			tPK			tPK tADA	tPK	tPK tADA	tPK	tPK ^a tADA ^a		
30 min (± 15 min) after end of infusion	tPK			tPK			tPK	tPK	tPK	tPK			
Post-treatment; not timed												tPK tADA	tPK tADA

tPK=tafasitamab pharmacokinetics; tADA = tafasitamab anti-drug antibodies; d = day; ; EOT = end of treatment

For pre-dose tPK and tADA, samples can be obtained up to 2 hours prior to the start of the infusion.

^a In all even-numbered cycles only.

Note: PK, and ADA samples are to be sent to the designated laboratories, per the laboratory manual, for analysis. All samples should be drawn within the time windows of the designated time and should be labeled with the exact, actual time of sampling.

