 - Concurrently use other anticancer or experimental treatments

Exclusionary Subject's Medical History

- Prior history of malignancies other than DLBCL, unless the subject has been free of the disease for \geq 3 years prior to screening. Exceptions to the \geq 3-year time limit include a history of the following:
 - Basal cell carcinoma of the skin
 - Squamous cell carcinoma of the skin
 - Carcinoma in situ of the cervix
 - Carcinoma in situ of the breast
 - Carcinoma in situ of the bladder
 - Tumor/Node/Metastasis [TNM] stage of T1a or T1b prostate cancer
- Subjects with the following medical history:

- Known active hepatitis infection:
 - Positive test for HBsAg or HBcAb (a subject whose HBsAg or HBcAb is positive may be enrolled if an HBV DNA test is negative and either the subject is treated with potent antiviral therapy or is re-tested for HBV DNA every month)
 - Positive test for HCV antibodies (a subject whose HCV antibody test is positive may be enrolled if quantitative HCV polymerase chain reaction test is negative)
- Known seropositivity for or history of active viral infection with HIV
- Positive SARS-CoV-2 nucleic acid or antigen test
- History or evidence of clinically significant cardiovascular, CNS, and/or other systemic disease that would in the Investigator's opinion preclude participation in the study or compromise the subject's ability to give informed consent
- History of solid organ transplantation
- History or evidence of rare hereditary problems of galactose intolerance, Lapp lactase deficiency, or glucose-galactose malabsorption
- Gastrointestinal abnormalities that would interfere with the ability to take or absorb oral medication

Dose, Route of Administration, and Treatment Regimen

Study Drugs:

Three study drugs are in use during this study: 1) Xencor study drug product DP /investigational medicinal product (IMP), plamotamab, and 2 other drugs previously approved by the FDA, 2) tafasitamab -cxix and 3) lenalidomide. The drugs will be used in triple combination, plamotamab (+) tafasitamab (+) lenalidomide.

- 1) Plamotamab (XmAb13676) is a humanized bsAb that binds both CD3 and the tumor antigen CD20 in order to recruit cytotoxic T cells to kill CD20 positive tumor cells. IV Solution Stabilizer (IVSS) is a concentrated form of the plamotamab (XmAb13676) buffer that also minimizes protein binding to the administration equipment when plamotamab is administered at lower concentrations.

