 - Have a history of deep venous thrombosis/embolism, threatening thromboembolism, or known thrombophilia, or are at high risk for a thromboembolic event in the opinion of the Investigator, and who are not willing/able to take venous thromboembolic event prophylaxis during the entire treatment period
 - Concurrently use other anticancer or experimental treatments

Exclusionary Subject’s Medical History

- Prior history of malignancies other than DLBCL, unless the subject has been free of the disease for \geq 3 years prior to screening. Exceptions to the \geq 3-year time limit include a history of the following:
 - Basal cell carcinoma of the skin
 - Squamous cell carcinoma of the skin
 - Carcinoma in situ of the cervix
 - Carcinoma in situ of the breast
 - Carcinoma in situ of the bladder

- Tumor/Node/Metastasis stage of T1a or T1b prostate cancer
- Subjects with the following medical history:
 - Known active hepatitis infection:
 - Positive test for hepatitis B surface antigen (HBsAg) or hepatitis B core antibody (HBcAb; a subject whose HBsAg or HBcAb is positive may be enrolled if a hepatitis B virus [HBV] DNA test is negative and either the subject is treated with potent antiviral therapy or is re-tested for HBV DNA every month)
 - Positive test for hepatitis C virus (HCV) antibodies (a subject whose HCV antibody test is positive may be enrolled if quantitative HCV polymerase chain reaction test is negative)
 - Known seropositivity for or history of active viral infection with human immunodeficiency virus (HIV)
 - Positive SARS-CoV-2 nucleic acid or antigen test
 - History or evidence of clinically significant cardiovascular, CNS, and/or other systemic disease that would in the Investigator’s opinion preclude participation in the study or compromise the subject’s ability to give informed consent
 - History of solid organ transplantation
 - History or evidence of rare hereditary problems of galactose intolerance, Lapp lactase deficiency, or glucose-galactose malabsorption
 - Gastrointestinal abnormalities that would interfere with the ability to take or absorb oral medication

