7.5.1. Screening Evaluations (Up to Day –35)

In Part 1, screening assessments are to be performed during the 28-day window prior to the priming dose of tafasitamab. In Part 2, screening assessments are to be performed within 28 days of randomization.

- Obtain signed informed consent (may be done up to Day –35)
- Review inclusion and exclusion criteria
- Medical history and physical exam (PE)
- Neurologic examination will be assessed using the ASTCT ICANS Consensus Grading for Adults (see [Section 4.6.1.7](#))

- Any cytogenetic information available on the tumor from time of original diagnosis and at transformation (if applicable) should be recorded, including cytogenetics, fluorescent in situ hybridization (FISH) analysis, and sequencing data
- Vital signs (supine or sitting position, including heart rate, blood pressure, temperature, respiratory rate, and blood oxygen saturation by pulse oximetry)
- Height, weight
- ECOG performance status (see [Appendix A](#), Performance Status Scale)
- Electrocardiogram (ECG), standard 12-lead, supine position
- Complete blood count (CBC): RBC, hemoglobin, hematocrit, mean corpuscular volume (MCV), RBC distribution width (RDW), white blood cell (WBC) with differential (neutrophils, lymphocytes, monocytes, eosinophils, basophils, myelocytes, promyelocytes; include percent and absolute, if reported) and platelet count
- Chemistry panel (sodium, chloride, potassium, bicarbonate, blood urea nitrogen, creatinine, glucose, uric acid, calcium, phosphorous, total bilirubin, ALT, AST, total protein, albumin, alkaline phosphatase, LDH, as well as serum gamma-glutamyl transferase [GGT], amylase, lipase, ferritin (screening only), and C-reactive protein (screening only))
- Coagulation panel (prothrombin time [PT]/international normalized ratio [INR] and activated partial thromboplastin time [APTT])
- Urinalysis with microscopy (pH, specific gravity, ketones, leukocyte esterase, bilirubin, blood, and protein; microscopy may include RBCs, WBCs, hyaline casts, RBC casts, WBC casts, granular casts, waxy casts [include microscopy findings in EDC only if reported])
- Hepatitis B (HBsAg, HBcAb, and HBsAb) and C (HCV), and HIV screening. These tests may have been performed within the previous 8 weeks.
- If HBcAb or HBsAg is positive, perform hepatitis B DNA testing. If subject is negative, subject may be enrolled if hepatitis B reactivation prophylaxis is initiated with entecavir, tenofovir, or lamivudine

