Laboratory Assessments: Safety laboratory assessments, including CBC with differential, chemistry panel, fibrinogen, coagulation panel, urinalysis, and pregnancy tests, may be completed up to 24 hours prior to the visit day. Excepted is the pregnancy test prior to the first dose of lenalidomide, which should be completed on Cycle 1 Day 1, within 24 hours of initiating treatment. Safety laboratory values, except for differential counts, fibrinogen, coagulation panel, and urinalysis, should be reviewed before starting study drug infusion.

- CBC with differential (absolute and percent), platelet count, and blast count, if reported (see [Section 7.5.1](#))
- Chemistry panel (see [Section 7.5.1](#))
- Fibrinogen
- If HBcAb serology is positive, HBsAg and hepatitis B DNA testing should be performed, with results available prior to dosing, on Day 1 of Cycles 2 and later, and at EOT (unless HBsAb is also present).
- Coagulation panel (prothrombin time PT/INR and APTT)
- Urinalysis (see [Section 7.5.1](#))
- Urine or serum β -hCG pregnancy test for women of childbearing potential should occur weekly during the first 4 weeks of lenalidomide, then on Day 1 of each subsequent cycles for dosing of plamotamab, tafasitamab, or lenalidomide. If menstrual cycles are irregular, the pregnancy testing should occur every 2 weeks during each subsequent cycle.
- The following are to be sent to the central laboratory per the laboratory manual:
 - Serum samples for plamotamab and tafasitamab ADA, cytokines, and plamotamab and tafasitamab PK (see [Table 10](#) and [Table 11](#) for collection schedule). All samples should be drawn within the window indicated on [Table 9](#) and of the designated time and should be labeled with the exact, actual time of sampling.
 - Peripheral blood for TBNK, leukocyte flow cytometry
 - Peripheral blood for RNA analysis

- Peripheral blood for ctDNA analysis
- Tumor biopsies (for those subjects who provided consent) collected once at follow-up (See [Section 8.2.2](#) and [Table 9](#))

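### Section 6.2 admits some hepatitis B-exposed subjects on monthly HBV DNA re-testing, but Table 9 footnote m leaves HBsAb-positive (and HBcAb-negative) subjects out of that re-testing

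*Protocol*

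**What the plan says.** The protocol deals with hepatitis B in four places.

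- **Entry (Section 6.2 and synopsis).** A subject positive for HBsAg or HBcAb may enroll if HBV DNA is negative and "either the subject is treated with potent antiviral therapy or is re-tested for HBV DNA every month". Nothing is said about HBsAb.
- **Screening (Section 7.5.1).** For the same DNA-negative subject, "subject may be enrolled if hepatitis B reactivation prophylaxis is initiated with entecavir, tenofovir, or lamivudine". No re-testing alternative is named.
- **Schedule (Table 9, row "HBsAg, Hepatitis B DNA ^m").** Footnote m says that "repeat testing should be performed only if HBcAb serology is positive and HBsAb serology is negative at screening". It places the draw 1 to 3 days before Day 1 of Cycle 2 and later cycles, so that the result is in hand before the dose.
- **Treatment cycles (Section 7.6.1).** "If HBcAb serology is positive, HBsAg and hepatitis B DNA testing should be performed", with timing given as "on Day 1 of Cycles 2 and later, and at EOT (unless HBsAb is also present".

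Section 7.2 allows prophylaxis with the same antivirals but does not require it. Section 5 says that Table 9 "defines the timing of study events and assessments", and also sends the reader to the protocol text for further detail.

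**The concern.** Under Section 6.2 the monthly HBV DNA test takes the place of antiviral cover. The schedule that sites work from does not provide that test for every subject whom Section 6.2 admits on that basis. A site that follows footnote m to the letter would omit it in an HBcAb-positive, HBsAb-positive subject who is not on antivirals.

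What is at stake is patient safety. All subjects receive tafasitamab, which Section 2.4.3 expects to deplete B cells, and the protocol itself treats hepatitis B reactivation as a risk that needs prophylaxis or monitoring. The chemistry panels and the liver rules in Table 8 pick up liver injury. They do not pick up a rise in HBV DNA before injury occurs.

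**Working it through.** The plan gives no figure to reproduce, so the check sets the rules side by side. Take a subject with negative HBV DNA at screening who is not on antivirals.

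| Serology at screening | Section 6.2 | Section 7.5.1, if prophylaxis is required | Footnote m | Section 7.6.1, read with footnote m |
|---|---|---|---|---|
| HBcAb+ / HBsAb− | may enter, monthly HBV DNA | may not enter | re-test each cycle | re-test each cycle |
| HBcAb+ / HBsAb+ | may enter, monthly HBV DNA | may not enter | no re-test | no re-test |
| HBsAg+ / HBcAb− | may enter, monthly HBV DNA | may not enter | no re-test | no re-test |

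**1. Where re-testing is scheduled, is it monthly?** Cycles are 28 days. Over the first 12 cycles, Day 1 of Cycles 2 to 12 gives 12 − 1 = 11 tests. The span is 12 × 28 = 336 days, and 336 / 30.44 = 11.0 months. So per-cycle testing meets the Section 6.2 duty for HBcAb+/HBsAb− subjects.

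**2. Where it is not scheduled.** For the other two rows the schedule gives 0 tests against about 11 implied by Section 6.2 over the same 12 cycles. Twelve cycles is only an illustration: it is the lenalidomide limit, and tafasitamab and plamotamab may continue until progression, so the shortfall continues for as long as treatment does.

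**3. When the draw falls.** One to 3 days before Day 1 is Day 28 to Day 26 of the preceding cycle (29 − 1 = 28; 29 − 3 = 26). Table 9 has a Day 26 ± 3 visit in Cycles 2, 4, 6 and later even cycles, but none at the end of odd cycles. Some added draws could therefore need a separate attendance.

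**4. How many subjects.** The documents give no serology frequencies. The lower limit is 0, reached if no subject entered on monitoring in either affected group. The upper limit is 3, the total enrolled according to SAP Section 1.

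**The case against.** The best defense is that Section 6.2 still binds. Section 5 refers sites to the protocol text, so the monthly duty exists even where the Table 9 row does not show it. Section 7.4 has the Medical Monitor or designee approve every subject before treatment. The exemption of HBsAb-positive subjects may also be deliberate. Part of this stands: the duty is not abolished. But footnote m says only if, which restricts testing rather than merely leaving it unmentioned. Approval at entry does not schedule later tests. If the HBsAb exemption is deliberate, Section 6.2 should carry it, and it would still not explain the HBsAg-positive, HBcAb-negative subject.

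A second objection concerns Section 7.5.1. Its wording can be read as stating one sufficient route, which agrees with Section 6.2. If it is read as mandatory, every such subject takes antivirals and the unmonitored, untreated subject cannot arise. This is right. A reader might infer that the entry conflict and the safety gap both hold at once, but they need opposite readings of 7.5.1. Under either reading some text needs correcting.

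Three further inferences are tempting and not supported:

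- **That 7.6.1 contradicts footnote m**, because its HBsAb exception might apply at EOT only. Read together, the two give the same rule.
- **That most eligible subjects are missed.** Six combinations of HBsAg, HBcAb and HBsAb satisfy Section 6.2 and footnote m covers two, but these are sign patterns, not shares of patients, and some are probably rare.
- **That the post-treatment test time is inconsistent.** Section 7.6.1 says EOT, while the mark in the Table 9 row appears under the 90-day visit. That rests on column alignment in extracted text, and the two times could both be intended. It is a query only.

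**Conclusion.** The mismatch is real and should be corrected. Section 6.2 and the synopsis make monthly HBV DNA re-testing a condition of entry without antivirals, whatever the HBsAb status. Footnote m, with Section 7.6.1, schedules it only for HBcAb-positive, HBsAb-negative subjects. The HBsAg-negative, HBcAb-positive, HBsAb-positive subject is enough to show the gap.

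The safety consequence assumes that the monitoring route is actually used and that the site follows the footnote rather than Section 6.2. In the study as run it can concern 0 to 3 subjects. It has no bearing on any endpoint, the type I error or the power. Confidence is high for the textual mismatch. Whether any subject was exposed to it cannot be told from the documents.

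**What to change.** Amend Table 9 footnote m and Section 7.6.1. Keep the existing testing of HBcAb-positive, HBsAb-negative subjects, and add that every HBsAg-positive or HBcAb-positive subject not on antiviral prophylaxis has HBV DNA tested for each cycle from Cycle 2 for as long as study treatment continues, whatever the HBsAb status, and at least monthly if a cycle is delayed. Keep the draw 1 to 3 days before Day 1, with the result available before dosing. Make Section 7.5.1 refer to the either/or condition in Section 6.2.

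If prophylaxis is meant to be mandatory, delete the monthly re-testing route from Section 6.2 and the synopsis instead.

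Ask the sponsor, as a query, whether the post-treatment HBV test belongs at EOT, at 90 days, or at both.

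The cost is wording plus about one extra blood draw per cycle for each affected subject, possibly as a separate draw before Day 1 where Table 9 has no visit at that time. If nobody uses the monitoring route, no tests are added. For the subjects already enrolled, it is enough to check their screening serology and HBV DNA follow-up against Section 6.2.
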